## 1. OVERVIEW

The purpose of the statistical analysis plan (SAP) is to ensure the credibility of the study results by pre-specifying statistical approaches for the analysis of this study. The SAP is intended to be a comprehensive and detailed description of strategy and statistical techniques to be used to realize the analysis of data for IMG-007-202. This SAP was written and finalized prior to the database lock, based on study protocol IMG-007-202 version 4 and 4.1(Canada only) (02 August 2024). Any methodological deviations from the protocol are documented. The analyses laid out in this SAP will be implemented by MeDaStats LLC for Inmagene Biopharmaceuticals.

### 1.1 Background and Rationale

Alopecia areata (AA) is a chronic relapsing and remitting autoimmune disease characterized by nonscarring hair loss involving the scalp, face, and/or body. It can affect children and adults of all ages, races and genders but more commonly in females and non-whites especially Asians. Approximately 2% of the general population can be affected by AA during their lifetime. The point prevalence rates of AA based on recent studies using electronic healthcare records were approximately 0.22% in the United States (US) and 0.58% in the United Kingdom.

AA typically presents with well-demarcated patches of hair loss, most commonly on the scalp, but it may also involve the beard, eyebrows, eyelashes, and nails. In severe cases, AA involves the full scalp (alopecia totalis [AT]) or even full body (alopecia universalis [AU]). AA involving 50% or greater scalp hair loss, including AT and AU, is considered an advanced form. AA is associated with other inflammatory and autoimmune diseases including atopic diseases (e.g., atopic dermatitis [AD] and allergic rhinitis), autoimmune diseases (e.g., thyroiditis, lupus erythematosus), metabolic syndrome, and psychiatric disorders. AA significantly impacts patients' daily life and often leads to profound psychological distress, social isolation, anxiety, and depression.

The exact pathogenesis of AA is not fully understood. It involves a complex interplay between genetics, environmental factors, and adaptive immune response to unknown antigens. It is thought that the collapse of follicular immune privilege leads to activation and infiltration of immune cells, primarily CD4+ and CD8+ T cells, and also natural killer cells, mast cells, and dendritic cells, which swarm and attack the hair bulbs. Hair follicle cells in turn release more cytokines and chemokines that further recruit T cells and other immune cells forming positive feedback loops that shorten and distort the hair cycle. Activation of T cell subsets including T-helper (Th) type 1 (Th1) and Th2 cells in AA patients is associated with disease severity or chronicity.

Current treatment options for AA are limited. They include topical, intralesional, and systemic agents. Topical treatments (e.g., topical corticosteroids, calcineurin inhibitors, diphenylcyclopropenone [DPCP], squaric acid, and minoxidil) have limited efficacy and are not suitable for large areas or long-term use. Intralesional corticosteroids are also not applicable for large areas and chronic use. Oral corticosteroids and conventional immunosuppressants (e.g., cyclosporine A, mycophenolate mofetil [MMF], and azathioprine) are used off-label, with limited evidence from randomized controlled trials regarding their benefit/risk profiles in AA patients. These immunosuppressive agents are often associated with adverse events (AEs)

that prevent their long-term use. Although oral Janus kinase (JAK) inhibitor baricitinib was recently approved by the US Food and Drug Administration (FDA) for severe and very severe AA, potential serious safety risks would limit its use for chronic management of AA. There remain significant unmet needs for safe and effective novel targeted systemic therapies for long-term treatment of AA.

Emerging evidence supports an important role of OX40– OX40 ligand (OX40L) signaling in promoting the proliferation and survival of T cells and augmenting the clonal expansion and function of effector and memory T cells, thereby mediating the pathogenesis of a spectrum of inflammatory and autoimmune diseases including AD and AA.

A genetic mapping study in AA patients revealed that an OX40L genetic locus is associated with susceptibility to AA. OX40L/OX40 interaction is required for the activation of CD4+ and CD8+ T cell as well as recruitment of other immune cells. In AA, activated T cells interact with other immune cells such as mast cells in amplifying follicular inflammation. Aggregation of peri- and intrafollicular OX40+ T cells and their physical contacts with OX40L+ mast cells were observed in AA hair follicles. Separately, elevated OX40 gene expression has been shown in AA lesional scalp.

## 1.2 Study Objectives

### 1.2.1 Primary Objective

To evaluate adverse events (AEs) emergent from multiple doses of IMG-007 in adult participants with alopecia areata (AA)

### 1.2.2 Secondary Objectives

To evaluate the efficacy of multiple doses of IMG-007 in AA participants as measured by severity of alopecia tool (SALT) at Week 24

### 1.2.3 Exploratory Objectives

- To further evaluate the efficacy of multiple doses of IMG-007 in AA participants as measured by SALT and other investigator's assessment and patient reported outcomes
- To further characterize the safety and tolerability of multiple doses of IMG-007 in AA participants

[figure not shown]
- To characterize the pharmacokinetic (PK) profile of multiple doses of IMG-007 in AA participants
- To evaluate the pharmacodynamic (PD) effect of IMG-007 on biomarkers in AA participants
- To evaluate the immunogenicity of IMG-007 in AA participants

## 2. INVESTIGATIONAL PLAN

### 2.1 Study Design

This is a phase 1b/2a, open label, dose escalation study to assess the safety, efficacy, PK, and PD of IMG-007 in alopecia areata (AA) participants. Approximately 30 participants will be enrolled. The study will consist of two dose cohorts to be initiated sequentially in ascending dose order: Cohort 1 with six participants receiving three Intravenous (IV) infusions of IMG-007 [REDACTED] over 4 weeks and Cohort 2 with 24 participants receiving three IV infusions of IMG-007 [REDACTED] over 4 weeks. [REDACTED]

Dose escalation decision would be made when all six participants in Cohort 1 have completed the Week 2/Day 15 visit, and all the safety and laboratory data have been reviewed by the Safety Review Committee (SRC). Adverse event (AE) severity will be evaluated according to the National Cancer Institute's (NCI) Common Terminology Criteria for Adverse Events (CTCAE) Version 5.0.

**Figure 1 Study Schema**

### 2.2 Sample Size Determination

A key secondary objective of the study is to explore the efficacy of IMG-007 treatment based on the percent change from baseline in SALT score at Week 24. [REDACTED]

## 2.3 Study Plan

The study consists of a screening period, a treatment period, a follow-up period, and an extended follow-up period.

### **Screening Period:** Day -35 to Day -1 (up to 5 weeks)

After providing informed consent, participants will be assessed for compliance with protocol requirements and study eligibility. Only in exceptional circumstances, when information concerning eligibility is outstanding (e.g., delayed laboratory results), will a longer screening period be permitted for up to three business days. Upon consultation with the medical monitor, a participant may be rescreened one time. Circumstances that may permit rescreening include, but are not limited to, a laboratory test result that does not meet eligibility requirements.

### **Treatment Period:** Day 1 (Baseline) to Day 113 (16 weeks)

Participants who meet all eligibility criteria will be enrolled and will receive three IV infusions of IMG-007 [REDACTED] or [REDACTED] administered 2 weeks apart at the Baseline (Day 1), Week 2 (Day 15), and Week 4 (Day 29) visits. The study site will contact participants by telephone approximately 24 hours after each infusion for assessment of AEs and/or concomitant medications.

On dosing days, study treatment will be administered as an IV infusion over approximately 60 minutes with a slower rate during the first 15 minutes. Participants will be closely monitored at the study site for a minimum of 1 hour after completion of each infusion or until any AEs observed during the observation have resolved or stabilized, whichever is longer. For diagnostic purposes, any participant who experiences any systemic infusion-related event should have a blood sample taken ideally 30–60 minutes after the onset for tryptase testing, and samples should be analyzed by a local laboratory if feasible. Study sites should have access to equipment or facilities for the management of potential hypersensitivity reactions.

Beyond dosing visits, participants will complete visits at Week 1 (Day 8), Week 6 (Day 43), Week 8 (Day 57), Week 12 (Day 85) and Week 16 (Day 113)/end of treatment (EOT).

### **Follow-up Period:** Day 113 to Day 169 (8 weeks)

The follow-up period consists of two visits: Week 20 (Day 141) and end of study (EOS; Week 24 [Day 169]) Visits.

### **Extended Follow-up Period Post EOS:** Day 169 to 253 (12 weeks)

The extended follow-up period after EOS consists of two visits: Week 30 (Day 211) and Week 36 (Day 253).

### 3. ANALYSIS SETS

The following analysis sets will be used for all statistical analyses covered within the scope of this analysis plan. There could be other analysis sets outside the scope of this SAP for dedicated purposes, such as population PK analysis.

The analysis sets defined below are based on guidance from the International Conference of Harmonization of Technical Requirements for Registration of Pharmaceuticals for Human Use (ICH) guideline ICH E9 Statistical Principles for Clinical Trials (1998).

#### 3.1 Safety analysis set

The safety analysis set includes all participants who received at least one dose of study treatment.

Safety analysis set will be used for analyses demographic and baseline characteristics, and safety data.

#### 3.2 Modified full analysis set

The modified full analysis set includes all participants who received at least one dose of study treatment.

Modified full analysis set will be used for all efficacy analyses.

#### 3.3 Pharmacokinetic analysis set

PK analysis set includes all participants in the safety analysis set and have baseline and at least one post-baseline evaluable data point. PK analysis set will be used for PK and ADA analyses.

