11 STATISTICAL CONSIDERATIONS

11.1 Sample Size Determination

11.2 Analysis Sets

- Safety analysis set will be used for safety analyses, which will include all participants who received at least one dose of study treatment. Participants will be analyzed by the dose received. Safety analysis set will also be used for demographic and baseline characteristics.
- Modified full analysis set will be used for efficacy analyses, which will include all participants who received at least one dose of study treatment.
- PK analysis set will be used for PK and ADA analyses, which will include all participants in the safety analysis set who also have baseline and at least one post-baseline evaluable data point.
- PD analysis set will be used for PD analyses, which will include all participants in the safety analysis set who also have baseline and at least one post-baseline evaluable PD/biomarker data point.

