11.3.4 Analysis of Immunogenicity

Samples to assess anti-IMG-007 antibodies will be collected for all participants and in sites that are able to adequately perform sampling, handling, and processing procedures outlined in the Laboratory Manual.

The immunogenicity results will be summarized using descriptive statistics by the number and percentage of participants who develop detectable ADA. The incidence of positive ADA will be reported for evaluable participants. The effect of immunogenicity on PK, efficacy and safety may be evaluated if data allows.

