## 5.11 Analysis of Immunogenicity Data

The ADA variables will be summarized using descriptive statistics by treatment in the immunogenicity analysis set. Frequency tables of the proportion of participants developing ADA positivity in the ADA assay, pre-existing ADA, treatment-emergent, treatment-boosted, persistent, indeterminate and transient ADA responses will be presented as absolute occurrence (n) and percent of participants (%), presented by treatment groups.

A listing of ADA data will be provided. The number and percentage of participants with ADA positive at each visit will be presented in the listing. The percentage will be based on the number of participants with ADA assessment at each visit.

The following summaries will be performed on the immunogenicity analysis set:

- Number (%) of patients negative ADA at all the time points analyzed by treatment group
- Number (%) of patients ADA positive at time points analyzed by treatment group
- Number (%) of patients with pre-existing ADA, treatment-emergent ADA, and treatment boosted ADA response by treatment group
- Number (%) of patients with persistent, transient and indeterminate treatment-emergent ADA response by treatment group
- Descriptive statistics of PK concentration in ADA positive and ADA negative participants by treatment group
- Descriptive statistics of dose adjusted PK concentration in ADA positive and ADA negative participants

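### The PK analysis set requires a baseline point that no planned PK concentration summary uses, so one unusable pre-dose sample can remove a participant's valid post-dose concentrations from the PK tables and figures

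*SAP*

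**What the plan says.** **PK set.** SAP 3.3: "PK analysis set includes all participants in the safety analysis set and have baseline and at least one post-baseline evaluable data point". Protocol 11.2 carries the same requirement: "PK analysis set will be used for PK and ADA analyses", limited to members of the safety set with a baseline and a post-baseline point. Neither text says whether the data point is a drug concentration or an ADA result.

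**PK outputs.** SAP 5.9 plans descriptive statistics of serum concentration by visit, the same by ADA status (also dose-adjusted), and mean and individual concentration-time figures. It also lists concentrations for each participant.

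**ADA.** SAP 3.3 assigns ADA analyses to the PK set, as the protocol does. SAP 5.11 uses another name: "The ADA variables will be summarized using descriptive statistics by treatment in the immunogenicity analysis set", and again "The following summaries will be performed on the immunogenicity analysis set". SAP Section 3 opens with "The following analysis sets will be used for all statistical analyses covered within the scope of this analysis plan", then defines only the safety, modified full, PK and PD sets. The explicit denominator in 5.11 is for positivity by visit: "The percentage will be based on the number of participants with ADA assessment at each visit". Protocol 11.3.4 says "The incidence of positive ADA will be reported for evaluable participants" and does not define the term there.

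**The concern.** A baseline requirement is useful when an analysis subtracts or conditions on the baseline. A concentration summary of an investigational antibody does neither: before the first infusion no study drug has been given, and the value enters no later statistic. The requirement therefore adds nothing to these outputs, but it can exclude a dosed participant whose later samples are all sound. In a cohort of six, one such exclusion is noticeable at every visit.

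The ADA wording adds a smaller problem. The overall ADA summaries are placed on a set with no definition, and the PK-by-ADA-status tables are listed in both 5.9 and 5.11 under different nominal sets. A programmer would have to guess the population.

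**Working it through.** The documents give no figure on this point, so there is none to reproduce. The check is a comparison of texts followed by counts.

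**1. Is there another baseline sample?** SAP 6.1 takes the latest valid value before dosing. The schedule of assessments (Protocol Table 1) and the sampling schema (Protocol Table 5) show no PK or ADA sample at screening. Day 1 pre-dose is the only scheduled one.

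**2. Samples at stake (SAP 4.7).** Scheduled PK samples: Day 1 pre-dose and end of infusion (2), Day 8 (1), Day 15 pre-dose and end of infusion (2), Day 29 pre-dose and end of infusion (2), then Days 43, 57, 85, 113, 141 and 169 (6). Total 2 + 1 + 2 + 2 + 6 = 13, of which 13 − 1 = 12 follow the first dose. Twelve is a maximum: it assumes that every later sample was collected and is evaluable.

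**3. Share per excluded participant (planned cohort sizes, SAP 2.1).**

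| Group | Scheduled post-first-dose samples | Share lost with one participant |
|---|---|---|
| Cohort 1 | 6 × 12 = 72 | 12/72 = 16.7% |
| Cohort 2 | 24 × 12 = 288 | 12/288 = 4.2% |
| Both | 30 × 12 = 360 | 12/360 = 3.3% |

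With the SD unchanged, the standard error of a visit mean grows by √(6/5) = 1.095 in Cohort 1 and √(24/23) = 1.022 in Cohort 2.

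**4. How likely is it?** The documents give no rate. As an assumption only, let each participant independently lack a usable pre-dose sample with probability p. The chance of at least one such participant among n is 1 − (1 − p)^n.

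| n | p = 2% | p = 5% | p = 10% |
|---|---|---|---|
| 6 | 11.4% | 26.5% | 46.9% |
| 24 | 38.4% | 70.8% | 92.0% |
| 30 | 45.5% | 78.5% | 95.8% |

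**5. Which ADA results need a baseline?** SAP 4.9 defines pre-existing, treatment-boosted and treatment-emergent responses by reference to baseline status or titre. Persistent, transient and indeterminate responses are subdivisions of treatment-emergent. The count of participants positive at any time point needs no baseline. One baseline rule for the whole ADA set would therefore be too strict for part of 5.11.

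**6. The parallel PD rule.** Protocol 11.2 asks for baseline and post-baseline data for the PD set. SAP 3.4 relaxes this to and/or. The PK rule was not changed in the same way.

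**The case against.** The strongest reply is that little is lost. The rule limits the set used for summaries, not the data: SAP 5.9 lists concentrations for each participant, SAP 6.3 puts all measurements in the listing, and Protocol 11.3.2 plans population PK/PD work under its own plan. The sample is taken in clinic within 60 minutes before dosing, so it should seldom be missing. The rule comes from the protocol, so the SAP did not introduce it. Because PK is also tabulated by ADA status, a common set has some logic. PK and ADA are exploratory objectives with descriptive analyses, so no test or error rate is affected. All of this stands and limits the size of the point. It does not give the baseline value a role in the concentration summaries, and a common set is needed only for the tables by ADA status.

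A reader might also infer that the SAP holds two conflicting ADA populations and that the ADA denominator is contradictory. The documents do not support that. There is no second definition. SAP 3.3 assigns ADA to the PK set, and the likeliest reading of 5.11 is an unharmonised label for that set. Taken alone, it is missing detail, and no numerical effect can be attached to it.

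**Conclusion.** The point holds as an inefficient inclusion rule with a simple remedy. As written, a participant without a usable Day 1 pre-dose sample leaves the PK summary tables and figures, with up to 12 valid post-first-dose concentrations: 1 of 6 participants in Cohort 1, 1 of 24 in Cohort 2. It would be too strong to say that the data are discarded, or that 12 concentrations are always lost.

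Two assumptions matter. First, the data point in 3.3 is read as a concentration. If either analyte were accepted, a usable Day 1 ADA sample would keep the participant in; if both were required, a missing ADA baseline would also remove PK data. Second, evaluability is taken to apply to the baseline as well; if it does not, only a missing sample excludes. The frequency of the event is unknown, and the probabilities above show only how they depend on an assumed rate. The undefined immunogenicity set is a secondary matter of harmonisation. The priority is low.

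**What to change.** - **SAP 3.3, PK set:** at least one dose and at least one evaluable post-dose IMG-007 concentration, with no baseline requirement. Name the analyte.
- **SAP Section 3, new ADA set:** at least one dose and at least one evaluable post-dose ADA result. Require an evaluable baseline ADA result only for the pre-existing, treatment-boosted and treatment-emergent categories, and state the denominator for those. Positivity at any time point then keeps participants without a baseline result.
- **SAP 3.3 and 5.11:** remove ADA from the uses of the PK set and refer to the ADA set by its defined name.
- **SAP 5.9 and 5.11:** state one population for the PK-by-ADA-status and dose-adjusted tables that appear in both sections. Otherwise the new sets could give the same table two populations.

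The cost is a few lines before database lock and no new data. The downside is a departure from Protocol 11.2, which must be recorded; SAP Section 1 already undertakes to document deviations in method from the protocol.

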#### 3.4 Pharmacodynamic analysis set

Pharmacodynamic (PD) analysis set includes all participants in the safety analysis set who also have baseline and/or at least one post-baseline evaluable PD/biomarker data point.

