## Version History

SAP Version	Date	Change	Rationale
1.0	25Oct2024	Not applicable	First version

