## 5.10 Analysis of Pharmacodynamic Data

### 5.10.1 Handling of PD data based on the prohibited medication use

All the PD assessments (except OX40 occupancy on CD4+ T cell and OX40+/CD4+ T cell in CD4+ T cell) will be treated similar to the secondary efficacy assessment for handling the intercurrent event (prohibited medication). That is, all PD assessments after the start date of first prohibited medication use of each participant will be set to missing. The results for OX40 occupancy on CD4+ T cells and OX40+/CD4+ T cells within CD4+ T cells will be used as collected.

Statistical analysis of the following pharmacodynamic variables will be presented.

- Listing of RO (%) by visit for individual
- Table and figure of RO (%) over time for each dose group
- Listing of Percentage of OX40+/CD4+ T cell in CD4+ T cell (%) by visit for individual
- Table and figure of Percentage of OX40+/CD4+ T cell in CD4+ T cell over time for each dose group
- Listing of Olink target 48 cytokine panel proteins levels in serum (pg/mL), by visit for individual (45 proteins)
- Table and figure of Olink target 48 cytokine panel proteins levels in serum (pg/mL) log10 transformed change from baseline over time for each dose group (45 proteins)
- Listing of Olink target 48 immune surveillance panel proteins levels in serum (pg/mL), by visit for individual (44 proteins)
- Table and figure of Olink target 48 immune surveillance panel proteins levels in serum (pg/mL) log10 transformed change from baseline over time for each dose group (44 proteins)
- Figure of baseline Th1/Th2/Th17/Th22 fold change vs healthy subject for individual
- Figure of baseline, Week 16 and Week 24 Th1/Th2/Th17/Th22 fold change vs healthy subject for each dose group
- Table and figure of IgE (IU/mL) log10 transformed change from baseline over time for each dose group
- Listing of levels of IgE for individual
- Listing of OX40 positive cells (cells/mm^2) in biopsy by visit for individual
- Table and figure of Week 24 LS (Lesion) vs Week 16 LS vs baseline LS vs baseline NL (non-lesion) OX40 positive cells in biopsy for each dose group
- Listing of OX40L positive cells (cells/mm^2) in biopsy by visit for individual
- Table and figure of Week 24 LS vs Week 16 LS vs baseline LS vs baseline NL OX40L positive cells in biopsy for each dose group
- Listing of Tryptase positive cells (cells/mm^2) in biopsy by visit for individual

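### SAP 3.4 widens the PD set beyond the protocol without recording it, and SAP 5.10 compares receptor-occupancy, T-cell and biopsy levels across visits with no same-participant rule

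*SAP*

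**What the plan says.** The protocol defines the PD set in the same words in its synopsis and in 11.2: participants in the safety set "who also have baseline and at least one post-baseline evaluable PD/biomarker data point". SAP 3.4 replaces the conjunction, so that "baseline and/or at least one post-baseline evaluable PD/biomarker data point" is enough. SAP 3.3, the neighbouring PK set, keeps the protocol's conjunction: "have baseline and at least one post-baseline evaluable data point".

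SAP section 1 states: "Any methodological deviations from the protocol are documented". The version history has one entry, marked "First version", with no change listed. The table of contents has no section on changes from the protocol, and no visible text mentions the PD set.

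The outputs in SAP 5.10 are of two kinds:

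- **Levels by visit.** Examples are "Table and figure of RO (%) over time for each dose group" and "Table and figure of Week 24 LS (Lesion) vs Week 16 LS vs baseline LS vs baseline NL (non-lesion) OX40 positive cells in biopsy". The percentage of OX40+/CD4+ T cells and the OX40L, tryptase, CD3, CD8 and FcEpsilonR1 biopsy counts follow the same pattern. No rule limits a comparison to people measured at both visits.
- **Change from baseline.** Serum proteins and IgE are tabulated as log10-transformed change, which needs both values from the same person.

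SAP 5.10.1 also sets PD values to missing once a participant starts prohibited medication. Receptor occupancy and the OX40+ T-cell percentage are exempt; biopsy counts are not.

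**The concern.** The study is open label with no control arm, so evidence of a tissue effect rests largely on comparison with baseline. If the baseline mean includes people who have no later value, or a later mean includes people with no baseline, a change in who is counted can look like a change in the biomarker. Cohort 1 has six participants, so one person can move a mean. Loss of biopsies need not be random: someone who starts prohibited medication before Week 16 supplies only baseline biopsy values to the analysis.

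The set definition is where a reader would look for protection against this. The SAP loosens it without saying so, and the text does not show whether the change was intended.

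**Working it through.** No figure in either document depends on the PD set, so there is nothing to reproduce. The check compares the two definitions and then asks how much the wording matters. Cohort sizes (6 and 24) are from protocol 4.1. The documents give no PD missingness rate, so every rate below is assumed and shown as a range.

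**1. Set membership.** Under *and/or*, three participants in Cohort 1 with baseline only and three with later values only would all be in the set, and the two means would share nobody. Under *and*, applied to that assay, none of the six would qualify.

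**2. One assay; baseline, Week 16 and Week 24; each value missing independently with probability p.**

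- Set size, *and/or*: 24(1 − p³). At p = 20%: 24 × 0.992 = 23.8.
- Set size, *and*: 24(1 − p)(1 − p²). At p = 20%: 24 × 0.8 × 0.96 = 18.4.
- Week 16 contributors with no baseline: p under *and/or*, 0 under *and*.
- Baseline contributors absent at Week 16: p under *and/or*, p/(1 + p) under *and*. At p = 20%: 0.20/1.20 = 16.7%.
- Week 16 contributors absent at Week 24: p under both.

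| p | Set size of 24: and/or; and | Week 16 without baseline: and/or; and | Baseline absent at Week 16: and/or; and | Week 16 absent at Week 24: both |
|---|---|---|---|---|
| 5% | 24.0; 22.7 | 5%; 0% | 5.0%; 4.8% | 5% |
| 20% | 23.8; 18.4 | 20%; 0% | 20.0%; 16.7% | 20% |
| 40% | 22.5; 12.1 | 40%; 0% | 40.0%; 28.6% | 40% |

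Applied per assay, the protocol's wording removes one mismatch, reduces a second and leaves the third alone.

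**3. Membership through any PD data.** Neither definition is assay-specific, so a person can qualify through blood and supply a biopsy at one visit only. Let biopsy be missing with probability p and blood with q = 5%. Week 16 biopsies without a baseline biopsy are p under *and/or* and p(1 − q)/(1 − pq) under *and*:

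- p = 10%: 10.0% against 0.095/0.995 = 9.5%
- p = 30%: 30.0% against 0.285/0.985 = 28.9%
- p = 50%: 50.0% against 0.475/0.975 = 48.7%

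Read literally, the change of wording hardly alters who enters the biopsy means.

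**4. What an unpaired mean can do.** Suppose a fraction f of baseline contributors have no later value, and their baseline mean exceeds that of the others by d. The baseline mean is then shifted by f × d. With assumed counts of 100 cells/mm2 at both visits in those with pairs and 160 in those with baseline only (d = 60):

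- Cohort 2, 4 of 24: (20 × 100 + 4 × 160)/24 = 110, an apparent fall of 10, or 10/110 = 9%.
- Cohort 1, 1 of 6: (5 × 100 + 160)/6 = 110, the same fall.
- f = 5%: shift 0.05 × 60 = 3. f = 40%: shift 0.40 × 60 = 24.

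If d is zero there is no distortion; if d is negative the table shows a false rise. The four baseline-only people in Cohort 2 would also be in the protocol's set if each had baseline and later blood samples, so the mean would be 110 under either wording.

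**The case against.** A reader might infer that the switch to *and/or* is what lets different people enter different visit means, and that restoring *and* would cure it. The documents do not support that. The protocol's definition is not tied to an assay and asks for only one later value, so mismatched means were possible under it too. Protocol 11.3.5 itself plans biopsy data summarized by visit, so the SAP did not introduce unpaired summaries. This part of the objection stands in full.

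There are also safeguards. SAP section 5 requires the number of non-missing observations with continuous summaries, and SAP 5.10 lists individual values by visit for receptor occupancy, OX40+ T cells and each biopsy marker. These make a changing denominator visible, and an interested reader could rebuild the pairs. They do not make the tabulated means comparable: equal numbers at two visits need not be the same people.

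A stricter set could also discard useful data. SAP 5.10 includes baseline lesional against non-lesional biopsy and individual baseline fold change against healthy subjects, and baseline-only participants belong in those. This stands, and it shapes the fix.

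Finally, some text cannot be seen. The content of SAP 4.8 and parts of protocol 7.5 are not visible, SAP 5.10 sends further PD work to a separate document, and the Canadian protocol version that the SAP cites was not available as a separate text. A pairing rule may exist there, so the finding is limited to the visible plan.

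**Conclusion.** The point holds in two parts. First, SAP 3.4 is broader than protocol 11.2, and the visible SAP does not record this despite its own statement about deviations. This needs no assumed numbers. Second, the receptor-occupancy, OX40+/CD4+ T-cell and biopsy tables compare levels across visits without a same-participant rule. The wording contributes to that gap but is not its sole cause.

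The size depends on missingness and on how far incomplete participants differ at baseline, and the documents give neither. The 110 against 100 example shows what unpaired means can do under assumed values; it does not estimate the effect of *and* against *and/or*. The importance is minor: the affected outputs are exploratory and descriptive, and no primary or secondary endpoint, sample size or error rate depends on them. Serum protein and IgE changes from baseline are not affected.

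**What to change.** - In SAP 3.4, either return to the protocol's definition or keep the broader one and record and justify it as a deviation.
- Define evaluability per assay, so that a blood sample does not make someone evaluable for biopsy.
- In SAP 5.10, base each baseline-against-visit comparison of receptor occupancy, OX40+/CD4+ T cells and biopsy counts on participants with evaluable values at both visits, and show the number of pairs. Do the same for Week 16 against Week 24.
- Keep all available values for listings and for within-baseline outputs (lesional against non-lesional, baseline against healthy).

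The cost is a few lines of SAP text and some table programming, with no new data. The downside is a smaller n in some exploratory PD tables, most noticeable in Cohort 1.
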